### **Determination of GCF Periostin, IL-17A, IL-17E Amount**

GCF Periostin, IL-17A, IL-17E levels were analyzed by the Sandwich ELISA method with the commercially available Human Periostin ELISA kit (Bioassay Technology Laboratory, Cat No. E3226Hu, Zhejiang, China), Human IL-17A ELISA kit (Bioassay Technology Laboratory, Cat No. E0047Hu, Zhejiang, China), Human Interleukin-25 ELISA kit (Bioassay

Technology Laboratory, Cat No. E0054Hu, Zhejiang, China) in Ondokuz Mayıs University Faculty of Medicine, Department of Medical Biochemistry Research Laboratory. The study data were converted to pg/mL30sec and statistical analyzes were made.

### **Statistical analysis**

SPSS for Windows Ver. for statistical analysis and graphics. 22.0 (SPSS Inc., Chicago, ILL, USA) and MS-Excel 2016 programs were used. Statistical significance level was accepted as p<0.05.

The normal distribution of the data in our study was evaluated with the Shapiro-Wilks test. The mean±standard deviation was used for the descriptive statistics for the normally distributed variables, and the median (min-max) value for the non-normally distributed variables. While examining the distribution of the gender variable in the groups, the result of the Chi-Square test was evaluated.

OneWay ANOVA test was applied to the variables showing normal distribution in the comparison of the data between groups. In post-hoc analyses, homogeneously distributed data according to Levene variance homogeneity test were evaluated with Tukey test, and data that were not homogeneously distributed were evaluated with Tamhane T2 test. Variables that did not show normal distribution were evaluated with the Kruskal-Wallis test. Bonferroni corrected Mann-Whitney U test was used in order to determine the group that caused the difference in the variables with a significant difference as a result of the Kruskal-Wallis test.

Paired-Sample T Test and Repeated Measured Analysis of Variance were used for the variables showing normal distribution in the evaluation of the within-group changes according to time. Significant differences as a result of analysis of variance were examined with Bonferroni, one of the multiple comparison tests. Variables that did not show normal distribution were analyzed with the Friedman test. The Wilcoxon test was used to determine the group that caused the difference in the variables with a significant difference as a result of the Friedman test.

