## **RESULTS**

### **Demographic Findings**

The distributions of gender and age of the groups were as follows: SP (seven male and four female subjects; mean age:  $40,9 \pm 9,28$  years); P (three male and eight female subjects; mean age:  $41 \pm 12,30$  years); SH (seven male and four female subjects; mean age:  $30,27 \pm 9,99$  years); H (three male and eight female subjects; mean age:  $26,36 \pm 4,20$  years).

The study groups were evaluated in terms of age and gender, and a significant difference was found between the groups in terms of mean age ( $\chi^2=16,567$ ; p=0.001). There was no

significant difference in terms of gender ( $\chi^2=0.364$ ;  $p=0.546$ ). The mean age of the H group was lower than the mean age of the patients in the SP ( $Z=18,000$ ;  $p=0.006$ ) and P groups ( $Z=16.682$ ;  $p=0.014$ ). It was determined that the mean age of the individuals was similar ( $Z=3,682$ ;  $p=1,000$ ) between group H and group SH.

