## **Biochemical Parameters**

### **GCF Periostin levels**

When the GCF Periostin data were examined, the difference between the groups was found to be statistically significant at the beginning ( $p=0.003$ ). In terms of periodontal disease, the amount of GCF Periostin in the P group was found to be significantly lower than in the H group ( $p=0.007$ ), while there was no statistically significant difference between the SP group and the SH group.

When evaluated in terms of smoking, it was observed that the GCF Periostin amount of the SP group was significantly higher than the P group ( $p=0.021$ ). There was no significant difference between the SH and H groups ( $p>0.05$ ).

A statistically significant difference was found between the groups on the 15th day ( $p<0.001$ ). When examined in terms of periodontal disease in the post-hoc analysis, it was found that the amount of GCF Periostin in the P group was significantly lower than in the H group, as at the beginning ( $p=0.002$ ). It was determined that there was no statistically significant difference between the SP group and the SH group. When evaluated in terms of smoking, it was observed that the GCF Periostin amount of the SP group was significantly higher than the P group ( $p=0.003$ ).

However, on the 30th day, it was determined that there was no statistically significant difference between the groups.

In the in-group evaluation of the change with treatment on a time basis, it was found that the GCF Periostin level in the SP group decreased over time ( $p<0.001$ ). In post-hoc analyzes, this decrease was observed to be significant between all times ( $p=0.009$ (0-15.days, respectively),  $p=0.001$ . (day 0-30) and  $p=0.003$ (day 15-30)). In the P group, there was no statistically significant difference in the evaluations of the 0th day, 15th day and 30th day within the group ( $p>0.05$ ).

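### Lower periostin in P than in H at days 0 and 15 is presented as a periodontal disease contrast, but P is 14.6 years older on average and no analysis adjusts for age

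*Combined protocol and SAP*

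**What the plan says.** The opening section, Study Protocol and Statistical Analysis Plan, selects four groups of 11 by disease and smoking status: SP, P, SH and H. It states no age matching, and the only age limit is a lower one of 18 years.

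The Statistical analysis section compares groups in one of two ways. In the first, "OneWay ANOVA test was applied to the variables showing normal distribution in the comparison of the data between groups", followed by Tukey or Tamhane T2. In the second, "Variables that did not show normal distribution were evaluated with the Kruskal-Wallis test", followed by Bonferroni-corrected Mann-Whitney tests. No ANCOVA, regression or stratification appears.

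Demographic Findings reports that "a significant difference was found between the groups in terms of mean age" (p=0.001) and, pairwise, that "The mean age of the H group was lower than the mean age of the patients in the SP" and P groups (p=0.006 and p=0.014). It finds no "significant difference in terms of gender" (0.364, p=0.546).

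GCF Periostin levels then reports for day 0: "In terms of periodontal disease, the amount of GCF Periostin in the P group was found to be significantly lower" than in H (p=0.007), "while there was no statistically significant difference between the SP group and the SH group". At day 15, P is again "significantly lower than in the H group, as at the beginning" (p=0.002). Age is not mentioned there.

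**The concern.** P and H differ in disease status and also, by a wide margin, in age. An unadjusted comparison cannot tell the two apart. Whichever branch periostin took, the P-H contrast carries the whole age difference.

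This matters because the two P-H periostin results are the only significant biomarker differences presented under periodontal disease. None is reported for periostin at day 30, or for IL-17A or IL-17E at any time.

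Day 15 is not an independent confirmation of day 0. The sampling text and the Treatment and Follow-up Protocol schedule repeat samples only for SP and P. Both contrasts therefore use the same 11 H samples and the same age gap.

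The direction of any bias is unknown. P-H is overstated if periostin falls with age and understated if it rises.

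**Working it through.** **Inputs from Demographic Findings (11 per group).** Mean age (SD) in years: SP 40.9 (9.28), P 41 (12.30), SH 30.27 (9.99), H 26.36 (4.20).

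**1. Reproducing the reported age tests.** Chi-square 16.567 on 3 df gives p=0.0009 (reported 0.001). The pairwise values labelled Z are mean-rank differences. Their standard error is sqrt(44×45/12 × 2/11) = sqrt(30) = 5.477.
- H vs SP: 18.000/5.477 = 3.29; p×6 = 0.0061 (reported 0.006).
- H vs P: 16.682/5.477 = 3.05; p×6 = 0.0139 (reported 0.014).
- SP vs SH, not reported: 18.000 − 3.682 = 14.318; 14.318/5.477 = 2.614; p = 0.0089; ×6 = 0.054.

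**2. Age gaps.** Pooled SD = sqrt[(9.28² + 12.30² + 9.99² + 4.20²)/4] = sqrt(88.71) = 9.42.

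| Contrast | Gap (years) | Gap in SD | Welch p |
|---|---|---|---|
| P-H | 14.64 | 1.55 | 0.003 |
| SP-SH | 10.63 | 1.13 | 0.018 |
| SH-H | 3.91 | 0.42 | 0.25 |
| SP-P | −0.10 | −0.01 | 0.98 |

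The Welch p values are uncorrected. SP-SH is weaker evidence of imbalance, given the Bonferroni p of 0.054 in step 1.

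**3. Shift in P-H due to age alone.** Shift = r × 1.554, where r is the size of the within-group age-periostin correlation. No value of r is given, so 0.1, 0.3 and 0.5 are assumptions. False-positive rates come from 100,000 simulated studies with the stated age means and SDs and no true group effect.

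| r | Shift (SD) | Tukey P-H | Kruskal-Wallis, then Dunn-Bonferroni |
|---|---|---|---|
| 0 | 0 | 1.0% | 0.6% |
| 0.1 | 0.16 | 1.6% | 1.0% |
| 0.3 | 0.47 | 6.6% | 4.4% |
| 0.5 | 0.78 | 21% | 15% |

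**4. Share of the reported difference.** If the p values are Tukey (4 groups, 40 df), the difference is q/sqrt(11). Day 0: 4.881/3.317 = 1.47 SD. Day 15: 5.506/3.317 = 1.66 SD. If periostin falls with age at r = 0.1, 0.3 or 0.5, age accounts for 11%, 32% or 53% at day 0 and 9%, 28% or 47% at day 15. Explaining all of it needs r = 1.472/1.554 = 0.95 at day 0, and 1.660/1.554 = 1.07, which is impossible, at day 15.

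**5. What adjustment could do to the p values.** Adding age multiplies the P-H variance by 1 + 14.64²/(40 × 88.71 × 2/11) = 1.33. The adjusted statistic is (difference − r × 1.554)/sqrt[2/11 × 1.33 × (1 − r²)]. Ranges run from a Tukey to a Bonferroni back-calculation, with periostin falling with age.
- Day 0: 0.024 to 0.029 at r = 0; 0.049 to 0.072 at 0.1; 0.16 to 0.30 at 0.3.
- Day 15: 0.009 to 0.011 at r = 0; 0.019 to 0.030 at 0.1; 0.069 to 0.14 at 0.3.

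**6. Disease by smoking.** P-H is significant and SP-SH is not, but the difference between the two was not tested. The section does not claim an interaction. Under Tukey, the day-0 p values (overall 0.003, P-H 0.007, SP-P 0.021) fit two solutions, with unadjusted interaction p = 0.0003 or 0.034. They lean towards an interaction but do not replace a test. This contrast carries a smaller age gap: 14.64 − 10.63 = 4.01 years.

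**7. Gender and grade.** The group counts sum to 20 men and 24 women. Testing 20:24 against 22:22 gives (2² + 2²)/22 = 0.364, p=0.546, which is the reported figure. It tests the total against an equal split and does not compare groups. The four-group test has expected counts of 5 men and 6 women per group: 4×(4/5) + 4×(4/6) = 5.87, 3 df, p=0.118. The 20:24 also conflicts with the 22 men and 22 women in the opening section. Separately, SP-P is presented under smoking although SP is defined as Grade C and P as Grade A.

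**The case against.** The strongest objection is that the documents' own results speak against age as the main driver. P is also significantly lower than SP, whose mean age is the same (p=0.021 at day 0, p=0.003 at day 15). Read as Tukey values, those differences are 1.29 and 1.60 SD, close to the P-H differences. SP-SH carries 10.63/14.64 = 73% of the P-H age gap. If a common linear age effect produced all of P-H at day 0, SP-SH should be about −1.07 SD, but the back-solved values are +0.89 or −0.15 SD. At day 30 the age gap is unchanged, yet no group difference is reported. All of this stands, and it is why age is judged unlikely to explain everything. It does not exclude partial bias in P-H.

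It can also be said that the disease wording only labels which pair is compared, and that the age imbalance is openly reported. That is fair, but nothing connects the two sections, so a reader of the periostin results is not warned.

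The sizes rest on an assumed correlation, and partly on the Tukey branch; the documents do not say which branch periostin took. That stands, and the sizes are given as conditional ranges.

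Comparisons of SH with H are described at days 15 and 30, which might suggest repeat sampling of healthy subjects. The sampling schedule, stated consistently elsewhere, provides it only for SP and P.

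Finally, sex is identical within each disease contrast (7:4 in SP and SH, 3:8 in P and H), so the gender points do not bear on P-H. They are minor corrections to the same comparisons.

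**Conclusion.** The concern holds and should be fixed. The absence of any age adjustment and the 14.64-year gap (1.55 SD) are certain. The size of the bias is not: it runs from 0.16 to 0.78 SD over assumed correlations of 0.1 to 0.5, in an unknown direction. Under the Tukey reading, and if periostin falls with age, that is roughly a tenth to a half of the reported difference. A modest negative correlation, about 0.1 to 0.3, would be enough to remove significance after adjustment at either day, partly through lost precision.

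The SP-P contrast is not confounded by age, and within-group changes over time are unaffected. The reported gender test does not compare the groups, and the sex totals conflict.

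**What to change.** - Beside the unadjusted results for periostin at days 0 and 15, and for day 30 and the other markers for completeness, report a linear model labelled post hoc, on the log scale if skewed. Include disease, smoking, disease by smoking, age and sex (38 residual df). Give the interaction and the P-H, SP-SH, SP-P and SH-H contrasts with 95% CIs.
- Report the age range of each group. State that P-H cannot be fully separated from age, and that days 0 and 15 share the same H samples.
- Describe SP-P as Grade C smokers versus Grade A non-smokers.
- Replace the gender test with the four-group test (5.87, 3 df, p=0.118). Note that 14/22 smokers and 6/22 non-smokers are male. Reconcile 20:24 with 22:22.

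**Cost.** A change of wording and a re-run on existing data, with no new samples. Precision falls. With age and sex in the model the P-H variance rises 1.34-fold and the SP-SH variance 1.18-fold. The P-H 95% CI half-width goes from 0.86 to 1.00 SD, or 0.95 and 0.87 SD if age explains the marker at a correlation of 0.3 or 0.5. A loss of significance would be ambiguous between lost precision and removed confounding.

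Age overlap is thin: P's mean lies 14.64/4.20 = 3.5 H-group SDs above H's. If ages are normal, only about 31% of P (3 or 4 of 11) would be below 34.8 years, H's mean plus 2 SD. The adjusted estimate therefore leans on the assumed form of the age effect and should be read as a sensitivity analysis. Only a large interaction could be shown: power is 36% at 1 SD, and 80% needs 1.74 SD.

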### **Study Protocol and Statistical Analysis Plan**

Before the study, One Way ANOVA test with a significance level of 5% was used for the sample size calculation. Based on this analysis, the sample size was determined as at least 11 people in each group and a total of 44 subjects to detect a difference between groups. This cross-sectional study was approved by Ondokuz Mayıs University Clinical Research Ethics Committee (OMUKAEK) Samsun, Turkey (protocol number; 2019/324).

Fourty four individuals, 22 males and 22 females who were older than 18 were enrolled in the study. The study groups were selected according to the following criteria from individuals who applied to the Ondokuz Mayıs University Faculty of Dentistry Periodontology Department Clinic for treatment or control, accepted to participate in the study, were systemically healthy, did not take any medication in the previous 6 months, and did not receive periodontal treatment in the previous 6 months:

Group 1: (SP) Stage 3 Grade C patients (n:11)

Group 2: (P) Stage 3 Grade A patients (n:11)

Group 3: (SH) Periodontally healthy smokers (n:11)

Group 4: (H) Non-smokers with periodontally healthy (n:11)

Individuals were included as smokers if they had smoked  $\geq 10$  cigarettes/day for  $\geq 5$  years, whereas individuals were included as nonsmokers if they had no previous history of smoking. The periodontitis stage III patients were evaluated clinically and radiographically, and were selected to have teeth with CAL  $\geq 5$  mm in at least 30% of them. Exclusion criterias were as follows; patients under the age of 18, pregnant or lactating women, patients who have a history of with systemic disease or cancer or chemotherapy and radiotherapy or ongoing drug therapy who might be affect the clinical characteristics of periodontitis, patients who smoke less than 10 cigarettes/day or who quit smoking.

In order to standardize the study, all radiological and clinical examinations were performed by a single investigator. In clinical examination, Plaque Index (PI), Gingival Index (GI), bleeding on probing (BOP), probing depth (PD) and clinical attachment loss (CAL) scores were measured and recorded from 6 regions of each tooth (buccomesial, midbuccal,

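### For non-normal variables, single-step Bonferroni over the six group pairs is valid but needlessly conservative; Holm gives the same error control and never rejects less

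*Combined protocol and SAP*

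**What the plan says.** The Statistical analysis section sets one threshold: "Statistical significance level was accepted as p<0.05". Comparisons between the four groups then follow one of two routes.

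- **Normal variables:** one-way ANOVA, then Tukey or, if variances differ, Tamhane T2 ("homogeneously distributed data according to Levene variance homogeneity test were evaluated with Tukey test").
- **Non-normal variables:** Kruskal-Wallis, then pairwise tests: "Bonferroni corrected Mann-Whitney U test was used in order to determine the group that caused the difference in the variables with a significant difference".

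The section does not give the number of comparisons in the Bonferroni correction and mentions no step-down method. The design has "at least 11 people in each group and a total of 44 subjects", so four groups give six pairs.

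Demographic Findings shows the second route applied to age. It prints a Kruskal-Wallis chi-square of 16.567 (p=0.001) and three pairwise results, all involving group H: H-SP (18.000, p=0.006), H-P (16.682, p=0.014) and H-SH (3.682, p=1.000). SP-SH, P-SH and SP-P are not printed.

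**The concern.** Single-step Bonferroni multiplies every pairwise p-value by six whatever its rank. Holm multiplies the smallest by six, the next by five, then four and so on, keeping the adjusted values in order. It holds the family-wise error at the same level under the same assumptions, rejects everything Bonferroni rejects, and sometimes rejects more. The usual reason to stay with Bonferroni is that it has matching simultaneous confidence intervals, but this document reports none.

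With 11 people per group, power is scarce. For any outcome on the non-normal route, the disease contrasts (SP-SH, P-H) and the smoking contrasts (SP-P, SH-H) rest on these adjusted p-values. Several conclusions in the results are statements that no difference was found, so power given up without a return matters.

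**Working it through.** **Inputs.** N=44 and n=11 per group (opening section); the three printed age statistics and the Kruskal-Wallis value (Demographic Findings); two-sided testing, which is assumed because the plan does not state sidedness. The age statistics are labelled Z but are far too large for the p-values beside them. They behave as differences in mean rank on the joint ranking.

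**Step 1: reproduce the printed p-values.** For a Dunn-type comparison, ignoring ties,

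SE = √[N(N+1)/12 × (1/n + 1/n)] = √[44×45/12 × 2/11] = √30 = 5.477, and z = difference/SE.

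| Pair | Difference | Raw p | ×6 | Printed |
|---|---|---|---|---|
| H-SP | 18.000 | 0.00102 | 0.006 | 0.006 |
| H-P | 16.682 | 0.00232 | 0.014 | 0.014 |
| H-SH | 3.682 | 0.501 | 1 | 1.000 |

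A multiplier of five would give 0.005 and 0.012 for the first two pairs, and four would give 0.004 and 0.009. The correction for age was therefore Bonferroni over all six pairs.

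**Step 2: check the reading of Z.** The four mean ranks average 22.5 and so sum to 90. Hence H = (90 − 3.682 − 18.000 − 16.682)/4 = 12.91, SH = 16.59, SP = 30.91 and P = 29.59. The Kruskal-Wallis statistic is 12/(44×45) × 11 × Σ(mean rank − 22.5)² = 16.53, against 16.567 printed; a tie factor of 0.9976 explains the gap. Placing SH below H instead would give 25.04, so the direction is settled.

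**Step 3: all six pairs under both corrections.** The unprinted SP-SH difference is 18.000 − 3.682 = 14.318, so z = 14.318/5.477 = 2.61 and raw p = 0.00895.

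| Pair | Raw p | Bonferroni (×6) | Holm factor | Holm |
|---|---|---|---|---|
| SP-H | 0.00102 | 0.006 | 6 | 0.006 |
| P-H | 0.00232 | 0.014 | 5 | 0.012 |
| SP-SH | 0.00895 | 0.054 | 4 | 0.036 |
| P-SH | 0.0176 | 0.106 | 3 | 0.053 |
| SH-H | 0.501 | 1 | 2 | 1 |
| SP-P | 0.810 | 1 | 1 | 1 |

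Only SP-SH crosses 0.05. With the tie correction it goes from 0.053 to 0.035, with the same result.

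**Step 4: does the crossing depend on the test?** Raw Mann-Whitney p-values cannot be recovered from the document. As a rough check, a t-test on the printed ages (SP 40.9 ± 9.28, SH 30.27 ± 9.99) gives SE = √[(9.28² + 9.99²)/11] = 4.11, t = 10.63/4.11 = 2.59 on 20 df, and raw p = 0.018. Bonferroni gives 0.106 and Holm (×4) 0.071. On that test the pair does not cross.

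**Step 5: power.** Simulations of four groups of 11 with normal data and assumed effects of 1.3 to 1.6 SD gave per-pair gains from Holm of roughly 1 to 8 percentage points. For example, one run of a 1.3-SD disease effect in both smoking strata went from about 46% to 52%. The effect sizes are assumptions, because the plan states none.

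**The case against.** The strongest reply is that nothing here is an error. Bonferroni controls the family-wise error, and choosing between valid procedures can be called taste. Bonferroni over only the four disease and smoking contrasts would also take SP-SH age to 0.00895 × 4 = 0.036. That Bonferroni is valid stands. The rest stands only in part: cutting the family to four pairs changes which hypotheses are protected, whereas Holm keeps all six and loses nothing in tests.

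A reader might go further and infer that real differences in the biomarkers were missed. The documents do not support that.

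- IL-17A and IL-17E show no group difference at any time, and periostin shows none on day 30. On the non-normal route, pairwise testing follows only a significant Kruskal-Wallis test, so Holm would have nothing to act on.
- For periostin on day 0, suppose the same Dunn-type test was used. Solving for mean ranks from the printed overall p (0.003), P-H (0.007) and SP-P (0.021) gives two solutions, and in neither does a pair cross 0.05 under Holm. In one, SP-SH is 0.17 to 0.37 and SH-H 0.10 to 0.24; in the other both are 1.
- Periostin on day 15 cannot be settled, because the overall result is printed only as p<0.001.

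A reader might also take the point to cover every group comparison. It does not: Tukey or Tamhane T2 handles normal variables, the within-group changes over time use other tests, and the documents do not say which outcomes were non-normal.

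Two further objections stand. The simulations use normal data, which the plan would send to ANOVA, so they show only the order of the gain. And moving to a less strict correction after seeing the results is a results-aware change; Holm's error guarantee is cleanest when it is chosen in advance.

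**Conclusion.** The point holds as an inexpensive improvement, not as a defect that invalidates anything. On the non-normal route, Bonferroni gives up a modest amount of power, roughly 1 to 8 points per pair under the assumed effects, with nothing gained in a report that gives no simultaneous intervals.

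The move from 0.054 to 0.036 for SP-SH age is an illustration. It concerns a baseline characteristic, is derived and not printed, and rests on reading the printed Z values as joint mean-rank differences. It overturns no printed statement: the only age similarity the text asserts is between H and SH, and the reported finding "The mean age of the H group was lower than the mean age of the patients in the SP" and P groups is significant under either correction.

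The same reading shows a mismatch that needs correcting in its own right: the age p-values reproduce under a Dunn-type joint-rank test, whereas the Statistical analysis section names Mann-Whitney.

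**What to change.** In the Statistical analysis section, for non-normal variables only:

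1. Replace the Bonferroni correction after Kruskal-Wallis with Holm-adjusted p-values over the six group pairs, and state that number.
2. Name the pairwise test actually run, Dunn-type or Mann-Whitney, so that the text and the age results agree.
3. In Demographic Findings, report all six age pairs and label the printed statistics correctly.
4. Because the results are already known, print the Holm values beside the Bonferroni values and mark them as post hoc.

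The cost is a sentence or two of wording and a re-ranking of raw p-values. Those raw values are not in the document, so the pairwise tests may have to be rerun. The one methodological downside is that Holm has no simple matching simultaneous confidence intervals, which would matter only if such intervals were added.

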### **GCF IL-17A levels**

In the analysis of GCF IL-17A values, no statistically significant difference was found between the groups in terms of both periodontal disease and smoking at any time ( $p>0.05$ ).

In the evaluation of the change with non-surgical periodontal treatment according to time, no statistically significant difference was found in the GCF IL-17A levels of the SP group between the baseline, the 15th day and the 30th day ( $p>0.05$ ). only in the P group, it was found that the GCF IL-17A level increased on the 30th day, with a statistically significant difference ( $p<0.05$ ). Significant differences were found between day 0 and day 30, and day 15 and day 30 in post-hoc analyzes ( $p=0.009$ ,  $p=0.005$ , respectively).

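### Change over time is tested only within SP and within P, so whether the two treated groups changed differently is untested for every GCF biomarker.

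*Combined protocol and SAP*

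**What the plan says.** The Statistical analysis section sets out two separate families of tests.

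- **Between groups:** one-way ANOVA or Kruskal-Wallis, with post-hoc tests. No change score and no group-by-time term is named.
- **Over time:** paired t test and repeated-measures ANOVA, or Friedman, used "in the evaluation of the within-group changes according to time". On the normal path, "Significant differences as a result of analysis of variance were examined with Bonferroni, one of the multiple comparison tests". On the non-normal path, "The Wilcoxon test was used to determine the group that caused the difference", with no correction stated.

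The results keep the same split. Under GCF Periostin levels, "it was found that the GCF Periostin level in the SP group decreased over time", with p=0.009 (day 0-15), p=0.001 (day 0-30) and p=0.003 (day 15-30). P shows no significant change. Under GCF IL-17A levels, "no statistically significant difference was found in the GCF IL-17A levels of the SP group" over the three visits, while "only in the P group, it was found that the GCF IL-17A level increased on the 30th day". For P, "Significant differences were found between day 0 and day 30, and day 15 and day 30 in post-hoc analyzes" (p=0.009 and p=0.005). On levels of IL-17A, "no statistically significant difference was found between the groups in terms of both periodontal disease and smoking at any time".

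**The concern.** A significant change in one group beside a non-significant change in the other does not test whether the two changes differ. The second group may have moved almost as far and just missed the threshold.

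Under the Treatment and Follow-up Protocol, SP and P are the only groups seen again after day 0. SP-P is therefore the only between-group contrast of change after treatment that this study can provide. It is neither planned nor reported. A reader who takes the IL-17A or periostin pattern as a difference in response has no estimate, interval or p-value to check it against.

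**Working it through.** **What the document gives.** It states no figure for the SP-P difference in change, so there is nothing to reproduce. The 11 per group comes from a one-way ANOVA calculation without stated power or effect size, and does not bear on this contrast. No biomarker means, medians, SDs or change scores are reported. What follows shows only which direct results the reported p-values would allow.

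**Inputs.** n=11 per group; significance level 0.05; IL-17A within P, p=0.009 (day 0-30) and p=0.005 (day 15-30); periostin within SP, p=0.001 (day 0-30); the other group not significant, exact p not given.

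**Assumptions.** Post-hoc p-values are two-sided paired-t p-values; SDs of change are equal in SP and P. The document does not make clear whether the p-values are Bonferroni-adjusted, so both readings are shown with one threshold used throughout each:
- unadjusted: p as reported; limit for the non-significant group 0.05;
- adjusted for three comparisons: p divided by 3; limit 0.05/3.

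**Formulas.**
- Standardised change: d = t(10 df)/√11.
- Direct test: t = (difference in d) × √(11/2) = (difference in d) × 2.345, on 20 df.
- 95% CI half-width: 2.086 × √(2/11) = 0.89 SD of change.

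**IL-17A, day 0-30, unadjusted.** p=0.009 gives t=3.231, so d=0.974 in P. The limit for SP is 2.228/√11 = 0.672.
- SP just short of significance, same direction: difference 0.302, t=0.709, p=0.49.
- SP unchanged: difference 0.974, t=2.285, p=0.033.
- SP just short of significance, opposite direction: difference 1.646, t=3.86, p=0.001.

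**IL-17A, day 0-30, adjusted.** 0.009/3 = 0.003 gives t=3.892, so d=1.173. The limit for SP is 2.870/√11 = 0.865.
- Same direction: difference 0.308, t=0.723, p=0.48.
- SP unchanged: t=2.752, p=0.012.
- Opposite direction: difference 2.039, t=4.78, p=0.0001.

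**Other comparisons, same method.**

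| Comparison | Reading | d in significant group | p, other group same direction | p, other group unchanged |
|---|---|---|---|---|
| IL-17A day 15-30 | unadjusted | 1.080 | 0.35 | 0.020 |
| IL-17A day 15-30 | adjusted | 1.284 | 0.34 | 0.007 |
| Periostin day 0-30 | unadjusted | 1.383 | 0.11 | 0.004 |
| Periostin day 0-30 | adjusted | 1.607 | 0.097 | 0.001 |

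**Sensitivity.** If the SD of change in SP were half or twice that in P (Welch test, adjusted reading, SP unchanged), the IL-17A day 0-30 p would be 0.003 or 0.10. Using normal instead of t quantiles on the unadjusted p gives z = 2.612/√2 = 1.847, p=0.065, with SP unchanged. With SP at z=1.96 it gives p=0.64.

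**Precision of the missing contrast.** At 11 per group a two-sided 5% two-sample t test has 80% power only for a difference of about 1.26 SD of change.

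**The case against.** The strongest reply is that nothing in the text is wrong. The IL-17A sentence sits in a paragraph on change within each group, and its restriction to P says which within-group test was significant. That is true as written. The preceding paragraph reports no group difference in levels at any visit. The study was sized by one-way ANOVA, is called cross-sectional, and states no hypothesis about differential response.

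Most of this stands, and it limits the point. A reader might infer that the document claims a different IL-17A or periostin response in SP and P. It draws no such conclusion, and the point is not that a stated inference is false. What remains is that the pattern invites that inference and offers nothing to test it.

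The level comparisons do not fill the gap. They compare groups at one visit, not change from day 0. This also applies to periostin, where SP exceeds P on days 0 and 15 and the groups do not differ significantly on day 30: moving from significant to non-significant across visits is again not a test of change.

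A second reply is that the illustrative figures are soft. That is fair. The non-significant results are given only as p>0.05 and may be omnibus results, so the pairwise limits used above are assumed. If Wilcoxon was used, the conversion through paired t is only approximate. The absence of an SP-P test of change does not depend on these figures.

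**Conclusion.** The gap is real: no SP-P comparison of change is described or reported for any outcome. For IL-17A and periostin the difference in change is untested, not shown to be absent. Under equal SDs and paired-t p-values, the direct p for IL-17A day 0-30 runs from about 0.48 or 0.49 down to 0.001 or less, and for periostin day 0-30 it starts at about 0.10 to 0.11.

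Two stronger readings are tempting and fail. One is that periostin can be set aside because its small p-values already establish a different change: with one threshold applied consistently, its upper value exceeds 0.05 on both readings, so the two markers should be treated alike. The other is that the IL-17A contrast is probably spurious: the same figures also fit clear evidence of a difference. Severity is minor to moderate, as a matter of analysis and reporting.

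**What to change.** For all three GCF biomarkers in SP and P, report the SP-P difference in change from day 0 to day 15 and from day 0 to day 30, each with a 95% CI. Use a group × time repeated-measures model (log scale if skewed) or change scores. That makes six contrasts. Label them post hoc and exploratory, and either run one group × time test per biomarker first or state a multiplicity correction. Covering all three biomarkers avoids choosing contrasts by their result. Base any statement of a different response on these contrasts. State also whether the reported post-hoc p-values are Bonferroni-adjusted.

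If this is not done, reword the periostin and IL-17A results as within-group only. For IL-17A: within P, levels were higher on day 30 than on days 0 and 15; within SP no significant change was found; change was not compared between groups.

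The cost is six contrasts on data already collected, or a few reworded sentences. The downside is imprecision: with a CI half-width of about 0.89 SD of change, an interval that includes zero would not show that the groups respond equally, and the report should say so.
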